## **3. STUDY DESIGN**

This is a multi-center, observational study involving retrospective collection of NSCLC patients information. All consecutive patients who had a newly diagnosis of NSCLC in 2017 from healthcare administrative database and received at least one anti-cancer drug treatment between January 2017 and December 2017, identified through the proposed algorithm, will be considered. All data needed for KPI calculation, even if they fall outside January-December 2017 period, will be collected. The end of data collection will be defined as patient death or 30 June 2018, whichever came first.

A set of potential KPIs had been developed from a panel of experts (clinicians, IT experts etc..) to investigate the appropriateness of activities within NSCLC care pathway, with a special focus on the use of immunotherapy.

The eligible population and data will be gathered retrospectively through an algorithm from administrative databases (SDO, REM, ASA, FED, AFT, ADI, SDHS-hospice).

Administrative data will be used as unique resource:

- to identify patients cohort;
- to measure KPIs along care pathway ;

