##### **4.1 Definition of study groups**

An algorithm will be developed to reliably identify eligible subjects from administrative database SDO. The algorithm will apply specific criteria to patients collected in administrative databases from January 2017 to December 2017. It will be developed as the combination of ICD-9-CM codes with other criteria. Selection of codes and criteria was based on a discussion between senior Oncologists with expertise in lung cancer and the outcome research working group at IRST.

A first data extraction from the administrative database will be performed to identified potential study subjects. These data are related to patients with at least one hospitalization due to diagnosis of malignant tumors of trachea, bronchi and lungs between January and December 2017 using the International Classification of Diseases, 9th EDITION, (ICD-9-CM codes: 162\* in all position of diagnosis codes).

The following criteria will be applied to obtained patients, to exclude prevalence NSCLC cases (incident cases in 2014-2016 period), patients with mesothelioma (cod 163\*) and SCLC patients in order to obtain the correct population.

- Only NSCLC incident cases in 2017 will be considered, excluding prevalence cases that had the same diagnosis in the 3 years before the period of interest (2014-2016). Patients with at least one hospitalization due to diagnosis of malignant tumors of trachea, bronchi and lung according to ICD-9CM 162\* in the 3 years prior to the first index hospitalization on the year of evaluation (2017) will be excluded

- Patients with at least one hospitalization due to malignant tumor different than tumors of trachea, bronchi and lungs (ICD-9CM 140\*-161\* or 163\*- 195\* or 200\* - 208\* or V.10\* excluding V10.11 and V10.12), in the 3 years previous 2017 should be excluded.
- All patients with at least one ATC Code L01CB01
- Etoposide (VP-16) therapy administration in the 180 days following the first hospitalization index will be excluded.

After criteria application, the final population shall include only NSCLC patients.

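### Section 4.1 tests for earlier disease only through hospital admissions, so patients diagnosed and drug-treated as outpatients before 2017 can enter as new cases; its etoposide rule for SCLC is ambiguous

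*Protocol*

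**What the plan says.** Section 4.1 builds the cohort from hospital discharge cards: "An algorithm will be developed to reliably identify eligible subjects from administrative database SDO". The first extraction takes 2017 admissions: "These data are related to patients with at least one hospitalization due to diagnosis of malignant tumors of trachea, bronchi and lungs", coded ICD-9-CM 162 in any diagnosis position.

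The incidence criterion then has an aim and a test.
- Aim: "Only NSCLC incident cases in 2017 will be considered, excluding prevalence cases that had the same diagnosis in the 3 years before". The years meant are 2014-2016.
- Test: the group removed is "Patients with at least one hospitalization due to diagnosis of malignant tumors of trachea, bronchi and lung according to ICD-9CM 162". The look-back is counted over 3 years, backwards from each patient's index admission.

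SCLC is removed through etoposide, in two consecutive bullets. The first names patients with at least one record of ATC code L01CB01 and gives no verb and no time limit. The second reads "Etoposide (VP-16) therapy administration in the 180 days following the first hospitalization index will be excluded". The section closes by stating that only NSCLC patients remain.

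Section 3 defines the target as a new NSCLC diagnosis in 2017 with at least one anti-cancer drug in that year. It lists the sources as "administrative databases (SDO, REM, ASA, FED, AFT, ADI, SDHS-hospice", which include outpatient care (ASA) and drug files (FED, AFT). Section 4.3 refers back to 4.1, and section 4.4 excludes only people living outside the region. Neither adds a look-back in the outpatient or drug data.

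**The concern.** The aim is about an earlier diagnosis, while the test is about an earlier admission. The two differ for anyone diagnosed and treated without being admitted. The drug files that could tell such patients apart are already study sources, and a drug code already helps to define the cohort, but section 4.1 sets no explicit search of them before the index admission.

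The primary objective is exposed because several indicators assume that the index admission lies near diagnosis.
- KPI 2 reads metastasis codes from the index hospitalization. A prevalent patient admitted for progression is counted as metastatic at diagnosis.
- KPIs 10 and 13 use the first administration of an anti-cancer drug. For these patients it happened before 2017.
- KPI 11a would mix later-line immunotherapy with treatment of new cases.

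The study looks at care among the participating sites. If sites differ in how often they treat without admission, the misclassified share differs too and could pass for a difference in quality.

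The etoposide rule raises a smaller question of the same kind: whether etoposide given before the index admission counts at all.

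**Working it through.** The protocol gives no figure to reproduce. Section 7.2 takes 400 as a feasibility count, without a power calculation. The check therefore applies the rules literally and then gives a range of sizes.

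**Step 1. The rules applied to example patients, index admission 1 June 2017.** The look-back for a 162-coded admission runs from 1 June 2014 to the index admission.

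| Patient | Bullets read as one sentence | Bullets read separately, L01CB01 at any time |
|---|---|---|
| A. Outpatient diagnosis and treatment in 2016, no earlier 162 admission | enters | enters |
| B. As A, but with a 162 admission in March 2016 | excluded | excluded |
| C. SCLC, outpatient etoposide September 2016 to January 2017 only, no earlier admission | enters | excluded |
| D. SCLC, etoposide in July 2017 | excluded | excluded |
| E. Diagnosed February 2017, outpatient treatment March 2017 | enters | enters |

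A is prevalent and enters under either reading. C is SCLC and enters only if the bullets are one sentence. E enters correctly as a 2017 case; only its index date is late. B shows that one coded admission in the look-back is enough to remove an outpatient.

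Section 3's drug requirement does not remove A if A also received a drug in 2017, as a patient starting a further line would. It does not remove C, whose etoposide ran into January 2017.

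**Step 2. Size.** Let f be the misclassified share of a KPI's denominator and d the difference between these patients and true incident cases on that KPI. Both are assumptions, because the documents give neither.

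- Patients affected = f × 400
- Observed KPI = (1 − f) × p + f × (p + d) = p + f × d, so the shift is f × d
- Highest attainable positive predictive value = 1 − f

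| f | Patients | PPV at most | Shift, d = 20 points | Shift, d = 40 points |
|---|---|---|---|---|
| 2% | 8 | 98% | 0.4 | 0.8 |
| 5% | 20 | 95% | 1.0 | 2.0 |
| 10% | 40 | 90% | 2.0 | 4.0 |

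As an illustration for KPI 11a, take 20% immunotherapy in true incident patients and 60% in pretreated ones. At f = 5% the result is 0.95 × 20 + 0.05 × 60 = 22%. At f = 10% it is 0.90 × 20 + 0.10 × 60 = 24%.

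**Step 3. Comparison with sampling error.** The 95% half-width is 1.96 × √(p(1 − p)/n). With n = 400 it is 1.96 × √(0.25/400) = 4.9 points at p = 0.5, and 1.96 × √(0.16/400) = 3.9 points at p = 0.2. Within the assumed range the shift lies mostly inside the interval and about equals it at the upper end for p = 0.2. KPI 11a counts only drug-treated, non-neoadjuvant patients, so its own interval is wider if that group is smaller than 400, and f there may differ from the cohort value. Unlike sampling error, the shift does not shrink with more patients.

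**The case against.** The best defence is that the algorithm is provisional. Section 4.2 validates it against IRST records and revises it to remove discrepancies. Section 7.3 counts patients who are incident in the administrative data but not in the chart as false positives. Patient A is such a false positive, and a revision made at IRST would carry over to the other two sites (section 2.2). This stands in part: validation may reveal the gap. It is not a stated rule, however, and it rests on IRST charts alone. Section 4.2 also speaks of applying the 4.1 criteria to the medical record; if that includes the admission test, the reference could share the blind spot.

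A second defence is that section 5 limits the data to 2017. It does not hold as a bar, because 4.1 itself needs 2014-2016 records and section 3 allows data from outside 2017.

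Three stronger readings are tempting, and the documents do not support them.
- A reader might infer that everyone treated as an outpatient before the first 2017 admission is misclassified. Patient E shows otherwise.
- A reader might infer that etoposide is certainly searched only after index. The separate L01CB01 bullet has no window and, taken alone, would catch etoposide at any time. What is shown is an ambiguity, which leaves a gap under one reading.
- A reader might take the share of lung cancer that is not NSCLC (10-15%, from the 85-90% in section 1) and derive a residual SCLC percentage. That would treat all other lung cancer as SCLC and would need an unsourced share with etoposide only before index.

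It also stands that the protocol does not say how many patients go 3 years without a 162-coded admission, or which day-care contacts the discharge database records as hospitalizations. Either could make the group small.

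**Conclusion.** The incidence gap holds on the text and under either reading of the etoposide bullets. The test in 4.1 cannot recognise disease diagnosed and treated before 2017 without a 162-coded admission in the look-back, and no other section does so. The etoposide point holds as a drafting defect: one reading misses SCLC patients whose etoposide ended before index, and the other leaves a criterion without verb or window.

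The size is unknown. With 2-10% of 400 misclassified and a 20-40 point difference, a KPI moves by about 0.4-4 points. Both ranges are assumptions. The study is descriptive, so no test result is at risk; what is at risk is the accuracy of KPIs 2, 10, 11a and 13 and, if the share varies by site, their comparison across sites. The change is worth making because it is cheap and uses sources already named.

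**What to change.** Two changes in section 4.1:

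1. Add an exclusion for patients with any anti-cancer drug (ATC L01) recorded in the administrative drug files from 1 January 2014 to 31 December 2016.
2. Replace the two bullets by one criterion: exclude patients with any L01CB01 (etoposide) record from 1 January 2014 to 180 days after the first index hospitalization. Since L01CB01 lies within L01, what this adds to change 1 is the stretch from 1 January 2017 to index and a clear end point.

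The drug look-back should be tied to the start of 2017 and not to the index admission. A window from 3 years up to 180 days before index, for example, would drop a patient diagnosed in January 2017, treated in February and first admitted in October, who is a true 2017 case. It would keep a patient first treated in October 2016 and admitted in February 2017, who is not.

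The cost is a drug-file extraction back to 2014, with the 2017-only sentence in section 5 reworded to allow it. A few patients given an L01 drug for a non-lung reason are lost. So are patients whose induction treatment began in late 2016, some of whom KPI 5 could otherwise count. Drugs given within clinical trials remain invisible, as the protocol notes under KPIs 5, 10 and 11. A patient diagnosed as an outpatient in 2016 with no recorded drug until 2017 would still enter, so the IRST chart comparison remains useful for judging what is left.

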#### **4.2 Validation of algorithm (only at IRST site)**

Algorithm will be validated against the electronic medical record review. Validation will be performed applying the criteria described in 4.1 paragraph on electronic medical record of patients treated in IRST. The population obtained from administrative database and identified by the algorithm as NSCLC or non-NSCLC will be then compared with the corresponding cases identified in the medical chart, and performance of the algorithm will be evaluated. The corresponding medical chart of the selected sample cases will be consulted only for validation purposes. The definitions of algorithm will be subsequently revised to maximize the agreement and delete discrepancies with the patient medical chart to maximize the accuracy of the algorithm.

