### **7.3 Data analysis**

For primary objective, for each indicator, the proportion of patients who receive the procedure, in the defined time window, among those eligible will be calculated. Descriptive statistics as arithmetic mean and standard deviation (SD) as well as median value and minimum–maximum statistics will be presented for KPI related to average time. Two-sided 95% confidence interval (95% CI) will be reported as appropriate and specified for KPI expressed as proportion. For secondary objective, the validity of algorithm will be evaluated by individual matching among cases retrieved from administrative database and medical chart obtained from IRST. Following definition will be used to explain this objective: NSCLC cases appearing as incident cases in administrative database, but not in IRST clinical chart will be considered as false positive and those appearing in IRST clinical chart but not in administrative database will be considered as false negatives.

Sensitivity will be defined as the percentage of NSCLC cases correctly identified by the algorithm and calculated as the proportion among NSCLC cases identified both in administrative database and IRST clinical chart ('true positive' cases) and all cases identified as NSCLC cases from IRST clinical chart ('true positive' + 'false negative' cases). Positive predictive value will be defined as the percentage of NSCLC patients identified from IRST clinical chart were really NSCLC. This proportion will be calculated as the proportion among NSCLC cases identified both in administrative database and IRST clinical chart ('true positive' cases) and all cases identified as NSCLC cases from administrative database ('true positive' + 'false positive' cases).

Likewise, specificity and negative predictive value will be calculated, and exact (Clopper-Pearson) 95% confidence limits for binomial distribution will be applied.

Statistical analysis will be performed using Stata software 15.1/SE for Windows (Stata Corp LP, USA).

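### Section 4.2 contradicts itself on the reference standard: it calls for chart review, but its only working rule re-applies the algorithm's own criteria to the chart

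*Protocol*

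**What the plan says.** Protocol section 4.2 makes three statements about the validation, in this order:

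- The standard to be used: "Algorithm will be validated against the electronic medical record review".
- The instruction for carrying it out: "Validation will be performed applying the criteria described in 4.1 paragraph on electronic medical record of patients treated in IRST".
- The comparison to be made: the algorithm's NSCLC or non-NSCLC result "will be then compared with the corresponding cases identified in the medical chart, and performance of the algorithm will be evaluated".

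The criteria referred to are in section 4.1. Entry requires "at least one hospitalization due to diagnosis of malignant tumors of trachea, bronchi and lungs between January and December 2017", identified by ICD-9-CM code 162*, which is a site code. Prevalent cases and patients with other malignancies, including mesothelioma, are then removed. SCLC is addressed by one rule, on ATC code L01CB01: "Etoposide (VP-16) therapy administration in the 180 days following the first hospitalization index will be excluded". Section 4.1 then closes with this claim about the result: "After criteria application, the final population shall include only NSCLC patients".

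Section 7.3 defines the error types by individual matching to the chart: "NSCLC cases appearing as incident cases in administrative database, but not in IRST clinical chart will be considered as false positive". False negatives are the reverse. The denominator of sensitivity is all NSCLC cases from the IRST chart. Neither 4.2 nor 7.3 says how a chart case is called NSCLC. Under section 2.2 the algorithm is then used at the other two sites from administrative data alone.

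**The concern.** A validation study needs a reference set independently of the test. The first and third statements in 4.2 point to such a reference, a chart review. The second, which is the only one that says what to do, points to the algorithm's own rules. These are different studies. One asks whether the algorithm finds NSCLC. The other asks whether two databases hold the same codes and drug records.

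The choice matters because IRST is the only site with charts, and so the only place where the purity asserted in 4.1 can be tested. The etoposide rule cannot guarantee that purity: it misses SCLC patients with no recorded etoposide and removes any NSCLC patient who received it. The algorithm population is also the denominator of KPIs 2, 3, 7, 15 and 16, so readers will rely on the validation results when they interpret those figures at all three sites.

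**Working it through.** **No figure to reproduce.** The protocol states no expected sensitivity or PPV, and section 7.2 gives about 400 patients as a feasibility count. The check is therefore a classification under each reading, followed by an illustration of size.

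**Step 1. The same patients under the two readings of 4.2.** Take patients who pass the other 4.1 criteria, and assume that both sources record the same etoposide data.

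| Patient | Reference: cell type in the chart | Reference: 4.1 rules applied to the chart |
|---|---|---|
| NSCLC, no etoposide in 180 days | true positive | true positive |
| NSCLC, etoposide in 180 days | false negative | true negative |
| SCLC, etoposide in 180 days | true negative | true negative |
| SCLC, no etoposide in 180 days | false positive | true positive |

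The two readings differ in rows 2 and 4. Moving row 4 from false to true positive raises PPV and specificity. Moving row 2 from false to true negative raises sensitivity and NPV. Every change is upward.

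**Step 2. Illustrative size of row 4.** Inputs:

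- s, the SCLC share of lung cancer: 10% to 15%. Section 1 gives NSCLC as 85% to 90%. Treating the whole remainder as SCLC, and applying it to patients hospitalised with code 162* at these sites, is an assumption.
- u, the share of SCLC with no recorded etoposide in 180 days: 20% to 40%. This is an assumption; the protocol gives no figure.
- Cohort: 400 (section 7.2).

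Residual SCLC share of the cohort = s·u / [(1 − s) + s·u]. This ignores NSCLC removed by the etoposide rule and every other source of error. PPV against cell type, from this source alone, is one minus that share.

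| s | u | Residual SCLC share | Of 400 | PPV against cell type |
|---|---|---|---|---|
| 0.10 | 0.20 | 0.02/0.92 = 2.2% | 8.7 | 97.8% |
| 0.10 | 0.40 | 0.04/0.94 = 4.3% | 17.0 | 95.7% |
| 0.15 | 0.20 | 0.03/0.88 = 3.4% | 13.6 | 96.6% |
| 0.15 | 0.40 | 0.06/0.91 = 6.6% | 26.4 | 93.4% |

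Widening u to 10% to 50% gives 0.01/0.91 = 1.1% (about 4 of 400) to 0.075/0.925 = 8.1% (about 32 of 400). The share is zero only if the etoposide rule catches every SCLC case.

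**Step 3. A condition that would reduce it.** Section 3 restricts the cohort to patients who received at least one anti-cancer drug in 2017. Sections 4.1, 4.3 and 7.1 do not repeat this. If it is enforced, untreated SCLC patients leave the cohort and only SCLC treated without recorded etoposide remains. The figures above would then be too high, by an amount the protocol does not allow one to calculate.

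**The case against.** The best defence is that an ordinary chart review is meant. Two of the three statements in 4.2 describe one. Sections 2.2 and 7.1 speak of a clinical database, and 7.3 matches individuals to the IRST chart and words PPV in terms of patients who really have NSCLC. Section 4.2 ends by planning to revise the algorithm until discrepancies with the chart disappear, which makes little sense if the chart case is built from the same rules. The disputed sentence may mean only that the aims of 4.1 (exclude prevalent cases, mesothelioma and SCLC) are applied when the chart is read. All of this stands as evidence of intent. It does not supply the missing definition: nowhere does the protocol name histology, cytology or the clinician's diagnosis as the basis for calling a chart case NSCLC, and the one rule it does give is the shared one.

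A reader might go further and infer that residual SCLC cannot be seen at all and that the PPV must come out at 100%. The documents do not support that. On a cell-type reading of the chart, such patients appear as false positives. Even on the literal reading, etoposide noted in the chart but absent from administrative data would show as a discrepancy; section 5.2 (KPIs 10 and 11) says trial therapies are missing from those data.

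A reader might also infer a known distortion of KPIs such as 2, 3, 15 and 16. None can be derived. For scale, with a 6.6% share and an assumed 30-point difference between SCLC and NSCLC patients, a KPI moves by 0.066 × 30 ≈ 2 points. The 95% half-width at n = 400 and 50% is 1.96 × √(0.25/400) ≈ 4.9 points.

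Finally, the closing sentence of 4.1 can be read as the intended result of the criteria. It is still worded as an outcome that the etoposide rule does not secure.

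**Conclusion.** The reference standard is contradictory in 4.2 and undefined in 7.3. Its only operational instruction is not independent of the algorithm. If that instruction is followed, all four accuracy measures are biased upward and largely describe agreement between data sources. The direction follows from the text, provided both sources carry the same etoposide records. The size does not: about 2% to 7% of the cohort as undetected SCLC is an illustration resting on an assumed SCLC share and an assumed etoposide gap, and it falls if the section 3 drug-treatment condition applies. The point concerns the secondary objective and should be settled before the charts are read. It does not show that the validation will fail or that any KPI is materially wrong.

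**What to change.** 1. In 4.2, replace the sentence that applies the 4.1 criteria to the chart. State that a reference case is a patient whose IRST record shows a histological or cytological diagnosis of NSCLC, first made in 2017, determined without the etoposide rule and without use of the algorithm result.
2. In 7.3, use the same definition for true and false positives and negatives.
3. In 4.1, describe the final population as algorithm-defined NSCLC in place of the assertion that no other cell type remains.
4. Report the chart-based IRST PPV, with the exact interval already planned, beside the KPIs. KPI estimates corrected for PPV are not needed: they would require KPI values among the false positives and would carry the IRST figure over to two sites without charts.

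The cost is amendment wording and a little abstraction. IRST charts are already to be consulted, so reading the recorded cell type adds little work. The reported accuracy may look somewhat less favourable.

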### ***2.2 Secondary Objectives***

The secondary aim is to develop and validate an algorithm to identify the eligible population of the study from administrative databases against to a clinical database (only at IRST site. Algorithm will be used to identify eligible patients and measure KPIs in the other two participating sites only through administrative database.

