#### **4.3 Inclusion Criteria**

[figure not shown]
4. Patients identified through the algorithm as described at paragraph 4.1;
5. Male or female;
6. At least 18 years at date of first index hospitalization;

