## **7. STATISTICAL CONSIDERATIONS**

### **7.1 Study design and objectives**

[figure not shown]
This is a multi-center, observational study involving retrospective collection of NSCLC patients information from regional administrative databases. All Patients identified through the algorithm as described at paragraph 4.1 will be considered.

Primary objective will be to measure a set of potential indicators (KPIs) derived from regional administrative database in order to investigate the appropriateness and quality of NSCLC care among participating sites.

The secondary aim will be to develop and validate an algorithm to identify the eligible population of the study from administrative databases against to a clinical database (only at IRST site).

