### **7.2 Population size**

Due to the descriptive nature of the study without a hypothesis testing, a formal calculation of sample size and statistical power was not performed. Considering a preliminary analysis of clinical

medical charts from previous years in participating centers, it will be feasible to include about 400 patients with defined characteristics as defined at 4.1 paragraph.

[figure not shown]

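### The protocol tests the 4.1 algorithm on the IRST charts and then revises it to fit those charts, without saying which version the accuracy figures describe or which version selects the KPI cohort

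*Protocol*

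**What the plan says.** - **4.1** lists the codes and exclusions that form the algorithm. They came from expert judgement: "Selection of codes and criteria was based on a discussion between senior Oncologists with expertise in lung cancer". The same section also says that the algorithm is still to be developed.
- **4.2** states that validation uses the 4.1 criteria on IRST patients. The result is "compared with the corresponding cases identified in the medical chart, and performance of the algorithm will be evaluated". The next step is: "The definitions of algorithm will be subsequently revised to maximize the agreement and delete discrepancies with the patient medical chart".
- **7.3** describes one matching exercise between administrative cases and IRST charts, with exact 95% limits. It refers only to the algorithm: "Sensitivity will be defined as the percentage of NSCLC cases correctly identified by the algorithm". It does not say whether this means before or after revision.
- **7.4** names the tasks that fill the study period. Work on discrepancies stands before statistical analysis, and no second validation is listed.
- **4.3** admits "Patients identified through the algorithm as described at paragraph 4.1", and **7.1** repeats: "All Patients identified through the algorithm as described at paragraph 4.1 will be considered".
- **2.2** carries the rule to the other hospitals, again without a version: "Algorithm will be used to identify eligible patients and measure KPIs in the other two participating sites only through administrative database".

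**The concern.** A rule adjusted until it agrees with a set of charts will look better on those charts than on new ones. An accuracy figure can be read as validation only if the rule was fixed before the charts were seen, or if the charts were not used to adjust it. The protocol plans both an evaluation and an adjustment on the same charts and does not tie the reported figures to either side of the adjustment.

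This matters for both objectives. Developing and validating the algorithm is the secondary objective. The algorithm also supplies the population for the primary KPIs: in 5.2, KPIs 2, 3, 7, 15 and 16 use everyone it identifies as the denominator. Section 6.3 limits Modena and Reggio Emilia to administrative data, so the IRST accuracy is the only evidence on misclassification there. A reader needs to know that it was measured for the rule that built the cohort.

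**Working it through.** The protocol states no accuracy target or sample size calculation, so there is no figure to reproduce. The check has two parts.

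**1. What each reading implies**

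| | Figures computed before revision (order of 4.2) | Figures computed after revision (possible from 7.4) |
|---|---|---|
| Cohort selected by the 4.1 rule (4.3, 7.1) | Figures match the cohort rule, no tuning bias; the revision plays no part in the study results | Figures describe a rule that did not select the cohort, and are optimistic |
| Cohort selected by the revised rule (possible from 2.2) | Figures unbiased, but for a different rule | Figures match the cohort rule, but are apparent accuracy |

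Only the top left cell gives a clean validation of the rule in use, and the text does not commit to it.

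**2. How large the optimism could be**

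Inputs:
- Total of about 400 patients (7.2). The IRST share is not given. Three equal sites would give 400 / 3 = 133. Assumed range: 100 to 200 true cases.
- Assumed: true sensitivity 85%, false-positive rate 25%, and 0.6 non-cases per case. Then PPV = 0.85 / (0.85 + 0.6 × 0.25) = 85%, specificity = 75%, and NPV = 0.45 / (0.45 + 0.15) = 75%.
- Assumed: K equally good variants with error correlation 0.5 to 0.8. The one with the best total agreement is kept and scored on the same charts (3,000 simulated runs per setting).

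Mean optimism in percentage points, 133 cases (range over the two correlations):

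| K | Sensitivity | PPV | Specificity | NPV |
|---|---|---|---|---|
| 3 | 1.3–1.6 | 1.1–1.5 | 1.7–2.3 | 2.2–2.7 |
| 5 | 1.7–2.1 | 1.6–2.0 | 2.4–3.2 | 2.9–3.6 |
| 20 | 2.8–3.5 | 2.5–3.1 | 3.9–5.0 | 4.7–5.8 |

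With K = 1 (no choice among variants) optimism is 0.3 points or less in every setting. Over 100 to 200 cases, coverage of the exact 95% interval for sensitivity is 95.0–97.3% with 2 to 5 variants and 88.2–92.9% with 20.

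Two harsher cases:
- Independent variants, true sensitivity 90%, best sensitivity kept, 133 cases: the mean apparent value is 92.9% with 5 variants (coverage 91.3%) and 94.6% with 20 (coverage 70.5%). Variants of one rule share most of their errors, so this overstates the effect.
- All discrepancies removed, which is the stated aim of 4.2: sensitivity reads 133/133 = 100%, with lower exact limit 0.025^(1/133) = 97.3%, whatever the true value.

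**3. What a held-out test would cost**

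Exact limits are the 2.5% quantile of Beta(x, n − x + 1) and the 97.5% quantile of Beta(x + 1, n − x).
- All 133 cases: 113/133 = 85.0% (77.7–90.6%).
- Half held out, 67 cases: 57/67 = 85.1% (74.3–92.6%).

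Typical error at a true 85%:
- Same charts: standard error √(0.85 × 0.15 / 133) = 3.1 points. With the bias for K = 5, the root-mean-square error is √(3.1² + 1.7²) = 3.5 to √(3.1² + 2.1²) = 3.7 points. This takes the standard error as unchanged by selection.
- Held-out half: √(0.85 × 0.15 / 67) = 4.4 points.

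With few variants, the split loses more precision than the bias it removes.

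**The case against.** The strongest reply is that 4.2 does name the tested rule: validation applies the 4.1 criteria, performance is evaluated, and only then are the definitions revised. Section 7.3 describes the same matching and need not repeat this. On that order the figures carry no tuning bias. This stands, and it rules out a stronger inference that a reader might draw, namely that the reported accuracy will be inflated. The documents do not establish that. They leave it open, because 7.4 puts the discrepancy work ahead of the analysis and 7.3 is silent.

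A second reply is that 4.3 and 7.1 are shorthand for whatever rule development produces, since 2.2 speaks of developing and validating an algorithm and 4.1 says that it will be developed. That may be the intention. But 4.1 sets out specific codes and exclusions, and nothing says that revised definitions replace them. If this reading is right, the rule that selects patients is one that no step tests.

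A third reply is that split samples and resampling are details for a statistical analysis plan. This stands as far as the missing hold-out goes, and a reader should not infer that a held-out sample is required; the figures above show that it can do more harm than good. The order of steps and the rule for eligibility are fixed in the protocol's own text, however, and these are what conflict.

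Finally, the KPIs are descriptive, and no decision depends on an accuracy threshold. This limits the consequences, but accuracy is itself a stated objective.

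**Conclusion.** The point holds as a gap in the protocol's own text. It does not show that an analysis error will occur. As written, the accuracy figures either describe the unrevised 4.1 rule, in which case they say nothing about a revised rule if that one is used, or they are computed after tuning and are optimistic. The text does not settle which.

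The true size cannot be known, because the protocol gives neither the IRST number nor the number of revisions. Under the assumptions above, a handful of variants costs about 1 to 2 points of sensitivity and 2 to 3 of specificity, with interval coverage near nominal. The effect becomes material only if many variants are tried or the charts are fitted completely. Nothing here shows that the KPI results themselves are wrong. Severity is minor to moderate.

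**What to change.** 1. In 4.2 and 7.3, compute and report sensitivity, PPV, specificity and NPV of the pre-specified 4.1 rule before any revision, and call this the validation result.
2. Report any figure for a revised rule on the same charts separately, labelled as apparent accuracy and not as validation.
3. In 4.2, 4.3 and 7.1, name the single version that selects the KPI cohort at all three sites. If it is the revised one, say that its validated accuracy was not measured.
4. Optional: freeze the revised rule and test it on IRST charts set aside at random before revision. This is worth considering mainly if many variants are expected. With few variants the loss of precision can exceed the bias removed.

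Items 1 to 3 are wording changes and need no new data. Their downside is that the stated accuracy may be slightly less favourable. Item 4 widens the interval (at 85%, from 77.7–90.6% on 133 cases to 74.3–92.6% on 67) and leaves fewer charts for revision.
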